6.1.4 Other Protocol-required Therapies

All other protocol-required therapies including dexamethasone and tocilizumab that are commercially available are not provided by Amgen. The investigator will be responsible for obtaining supplies of these protocol-required therapies.

Dexamethasone:

Premedication with dexamethasone is required prior to each AMG 330 treatment cycle and prior to each dose step for the prevention of CRS. Dexamethasone should be administered as a single IV dose (8 mg) within 1 hour of start of AMG 330 infusion or dose step, respectively. Dexamethasone will not be given as a premedication prior to pembrolizumab administration.

Approved

In the case of re-start of AMG 330 infusion after an infusion interruption of > 24 hours, dexamethasone (8 mg IV) should be administered within 1 hour prior to re-start and within 1 hour prior to the dose step.

For administration of dexamethasone after occurrence of CRS or other immune related adverse events, follow guidance in [Section 6.8](#) and [Table 6-3](#).

Tocilizumab:

For administration of tocilizumab after occurrence of CRS, follow guidance in [Section 6.8](#).

Throughout the study, Investigators may prescribe any concomitant medications or treatments deemed necessary to provide adequate supportive care except for those listed in [Section 6.1.7](#). Supportive care may include premedication with anti-emetics to limit treatment-related nausea and vomiting. Subjects should receive medications for treatment-induced diarrhea as clinically indicated. Anti-inflammatory or narcotic analgesics may be offered as needed. Packed red blood cell and platelet transfusions should be administered as clinically indicated.

Concomitant therapies are to be collected from the day of signing the informed consent, through the end of study. For all concomitant therapies collect therapy name, indication, dose, unit, frequency, route, start date, and stop date.

6.1.5 Other Treatment Procedures

Not applicable

6.1.6 Product Complaints

A product complaint is any written, electronic or oral communication that alleges deficiencies related to the identity, quality, durability, reliability, safety, effectiveness, or performance of a drug(s) or device(s) after it is released for distribution to market or clinic by either Amgen or by distributors and partners for whom Amgen manufactures the material.

This includes any investigational/non-investigational product(s), device(s) or combination product(s) provisioned and/or repackaged/modified by Amgen including AMG 330 and pembrolizumab.

Any product complaint(s) associated with an investigational product(s), non-investigational products(s), devices(s), or combination product(s) supplied by Amgen are to be reported according to the instructions provided in the IPIM.

6.1.7 Excluded Treatments, Medical Devices, and/or Procedures During Study Period

Any antitumor therapy other than the investigational product, including cytotoxic and/or cytostatic drugs, hormonal therapy, immunotherapy or any biological response modifiers, any other investigational agent, chronic systemic corticosteroid therapy, other immunosuppressive therapies, or HSCT is not allowed during screening and during the study treatment period until end of study. Exception: Hydroxyurea is allowed to control blasts as described in [Section 6.7.2](#).

Radiotherapy is not permitted during screening and during the study treatment period until end of study except for palliation of symptoms and should be approved by Sponsor. Investigators should ensure that the need for radiation does not indicate progressive disease and that for subjects with measurable disease, radiation is not to the sole site of measurable disease.

Medications or vaccinations specifically prohibited in the exclusion criteria are not allowed during the study. If there is a clinical indication for any medication or vaccination specifically prohibited during the study, discontinuation from study therapy or vaccination may be required. The investigator should discuss any questions regarding this with the Sponsor. The final decision on any supportive therapy or vaccination rests with the investigator and/or the participant's primary physician. However, the decision to continue the participant on study treatment requires the mutual agreement of the investigator, the Sponsor and the participant.

Listed below are specific restrictions for concomitant therapy or vaccination during the course of the study:

- Antineoplastic systemic chemotherapy or biological therapy
- Immunotherapy not specified in this protocol
- Chemotherapy not specified in this protocol
- Investigational agents other than pembrolizumab
- Live vaccines within 30 days prior to the first dose of study treatment and while participating in the study. Examples of live vaccines include, but are not limited to, the following: measles, mumps, rubella, varicella/zoster, yellow fever, rabies, BCG, and typhoid vaccine. Seasonal influenza vaccines for injection are generally killed virus vaccines and are allowed; however, intranasal influenza vaccines (eg, FluMist®) are live attenuated vaccines and are not allowed.

The following procedures should also not be undertaken within the timeframes specified prior to enrollment and during the study:

- Participation in an investigational study (drug or device) within 14 days of study day 1 and during the study
- Major surgery within 28 days of study day 1 (with the exception of biopsy or long line insertion)

6.2 Dose Modification

6.2.1 Dose-cohort Study Escalation/De-escalation and Stopping Rules, Dose-Limiting Toxicities (DLTs)

Step Dose Level Determination

A decision to proceed with the next step dose of AMG 330 for each subject in cohorts 1 and 2 will be based on investigator's assessment of safety and upon approval by Sponsor.

In cohort 1, a sentinel subject will be treated first. The minimal interval between treatment start for the sentinel subject and other subjects in the cohort is 21 days. If the sentinel subject has not experienced a DLT by day 14 at █ µg/day AMG 330, he/she will proceed with 200 mg pembrolizumab on day 15 and remain at an AMG 330 dose level of █ µg/day for 7 days (until day 21). If the sentinel subject experiences a DLT during the first 7 days of treatment with AMG 330 at █ µg/day, this subject will be replaced, but the DLT will still be counted towards the study stopping rules. If the sentinel subject does not experience a DLT before or on day 21, the next subjects in the cohort may initiate dosing. If a sentinel subject experiences a DLT, the sponsor will issue a decision based on the evaluation of clinical significance of the adverse event by the DLRT and potential decisions by the sponsor may include stopping AMG 330 and/or pembrolizumab, dose de-escalation of AMG 330, or continuing therapy at full dose.

Cohort 2 will be initiated only after all subjects in cohort 1 completed study day 28 (ie, AMG 330 █ µg/day dose level in combination with pembrolizumab for 7 days), and if the rate of DLT is ≤ 3 out of 10 subjects. After receiving the DLRT recommendation, sponsor will render a final decision and will issue a written notification of the decision to investigators. Further information on dose level review meetings (DLRMs) is provided in [Section 11.3](#).

Individual Stopping Rules

Dosing for an individual will be stopped for any occurrence of a DLT. The event will be reviewed by the investigator and Sponsor for evidence of relationship to treatment and

clinical or medical significance to decide whether dosing may be resumed for the individual and any modifications to the dosing, if appropriate.

Dose Limiting Toxicities

A DLT will be defined as any of the events described below occurring in a subject during the DLT window, unless clearly attributable to causes other than investigational product. The DLT window will start on day 1 and last for the duration of cycle 1. The CTCAE v5 will be used to assess toxicities/adverse events with the exception of CRS (see [Table 6-5](#) for grading of CRS).

DLT Evaluation

To be DLT evaluable, subjects must meet 1 of the following criteria during DLT evaluation period (cycle 1 day 1 to cycle 1 end of infusion):

- The subject experienced a DLT; OR
- The subject has received at least 70% of planned cumulative dose of AMG 330 and has not missed more than 1 dose of pembrolizumab; OR
- The subject did not experience a DLT and completed the DLT evaluation period

Events listed below are to be considered as DLTs and exceptions when occurring in a subject during the DLT window unless clearly attributable to causes other than AMG 330 and pembrolizumab treatment:

- Any treatment-related death.
- Grade 4 neutropenia lasting \geq 4 weeks from last day of cycle in absence of evidence of active AML. Note: grade 4 neutropenia maybe assessed retrospectively and outside of the DLT window
- Grade 3–4 non-hematologic toxicity not clearly resulting from the underlying leukemia EXCEPT:
 - Grade 3 fatigue, asthenia, fever, anorexia, or constipation
 - Grade 3 nausea, vomiting or diarrhea not requiring tube feeding, total parenteral nutrition, or requiring or prolonging hospitalization
 - Infection, bleeding, or other expected direct complication of cytopenias due to active underlying leukemia
 - Grade 3 infusion reaction, unless attributed to pembrolizumab, if successfully managed and which resolves within 72 hours
 - Grade 3 rash or pruritus
 - Grade 3 or 4 tumor lysis syndrome if it is successfully managed clinically and resolves within 7 days without end-organ damage.

Approved

- Grade 3 or 4 isolated analyte abnormalities (ie, those occurring without clinical consequence) that resolve, with or without intervention, to < grade 2 levels in < 72 hours will not be considered DLT.
- Grade 3 or 4 asymptomatic enzyme elevations including aspartate aminotransferase (AST), alanine aminotransferase (ALT) (without bilirubin elevation), gamma glutamyl transferase that resolve, with or without intervention, to ≤ grade 2 within 7 days will not be considered a DLT, unless attributed to pembrolizumab.
- Isolated grade 3 elevation of amylase or lipase not associated with clinical or radiological evidence of pancreatitis
- Grade 3 endocrinopathy that is well controlled by hormone replacement
- CRS meeting any of the criteria listed below:
 - Grade 2 CRS that does not resolve, with or without intervention to grade 1 within 7 days will be considered a DLT
 - Grade 3 CRS that does not resolve, with or without intervention to ≤ grade 2 within 5 days, will be considered a DLT
 - Any grade 4 CRS
- Any grade 5 toxicity
- Receive less than 70% of the planned cumulative dose of AMG 330 or miss more than 1 dose of pembrolizumab during the first cycle due to investigational product(s) related toxicity that does not meet the DLT criteria listed above

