4.1 Overall Design

This is a phase 1b study assessing safety, tolerability, PK, pharmacodynamics, and efficacy of AMG 330 administered as clV infusion in combination with pembrolizumab in adult subjects with R/R AML.

The study is a non-randomized study and will consist of 2 sequential dosing cohorts. Both cohorts will include AMG 330 and pembrolizumab with the difference being the initiation date for pembrolizumab treatment.

This study will use a staggered enrollment approach. Subject enrollment will start with cohort 1 ([Section 4.1.1](#)). The first subject dosed in cohort 1 will serve as the sentinel subject. Subsequent subjects dosed in cohort 1 will start AMG 330 (█ µg/day) administration once sentinel subject has cleared the study day 21 dose (AMG 330 monotherapy at █ µg/day). Per sponsor determination, if the sentinel subject does not experience a dose-limiting toxicity (DLT) on days 15 to 21 after pembrolizumab is administered, the other subjects in cohort 1 will be allowed to continue the planned treatment schedule. If the sentinel subject experiences a DLT during days 15 to 21, the dose level review team (DLRT) will discuss the case and the decision will be made by the sponsor based on clinical assessments of the adverse event and potential decisions by the sponsor may include stopping AMG 330 and/or pembrolizumab, dose de-escalation of AMG 330, or continuing therapy at full dose. Investigators and sponsor will meet after all subjects in cohort 1 have completed study day 28 (ie, AMG 330 █ µg/day dose level in combination with pembrolizumab) to assess the safety profile. If pre-specified safety criteria are met (≤ 3 out of 10 treated subjects in cohort 1 experienced DLT by day 28), subjects enrolled in cohort 2 ([Section 4.1.2](#)) may proceed with the treatment schedule. Similar to cohort 1, the first subject dosed in cohort 2 will serve as the sentinel subject. Per sponsor determination, if the sentinel subject does not

experience a DLT during the first 7 days, the other subjects in cohort 2 will be allowed to continue the planned treatment schedule.

Safety data will be continuously monitored throughout the whole treatment period. Sponsor in consultation with investigators may reconvene to make appropriate safety measures and adjustments as needed.

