9.4.1 Planned Analyses

9.4.1.1 Interim Analysis and Early Stopping Guidelines

Safety data will be reviewed on an ongoing basis. A DLRM will occur when at least 10 treated subjects in cohort 1 have been dosed through study day 28 to determine if the safety profile of initial steps in cohort 1 is acceptable to begin enrollment of cohort 2 or if the study should be stopped. If 3 or more of the 10 treated subjects in cohort 1 experience a DLT by day 28, the guidance to the DLRT is to recommend not to initiate cohort 2. The stopping rule is based on having at least a posterior probability of > 70% that the DLT rate is > 20% assuming a prior distribution of Beta (0.40, 1.60). If the true DLT rate is 10%, 20%, 30%, 40%, or 50%, then the probability of stopping the study at the interim analysis is 7%, 32%, 62%, 83%, 95%, respectively.

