11.3 Appendix 3. Study Governance Considerations

Dose Level Review Meetings

In this study, a dose level review meeting (DLRM) will be conducted 1 time to review and interpret safety data for the purposes of making recommendations about opening cohort 2 and evaluating safety signals for purposes of applying dose cohort/individual stopping rules. The Dose Level Review Team (DLRT) will meet to confirm the decision rules when the following criterion is met:

- at least 10 treated subjects in cohort 1 have been dosed through the end of [REDACTED] µg/day Step Dose (study day 28).

The required DLRT members are the Early Development Lead, Medical Monitor, Global Safety Officer (GSO), and Site Investigators. The DLRT will also include the Early Development Medical Director (Merck) in an advisory role. The DLRT will include Site Investigators from activated sites. The Early Development Lead, Medical Monitor, GSO, and Site Investigators are the only voting DLRT members. The following non-voting Amgen representatives may also be part of the DLRT: clinical study manager, biostatistician, pharmacokinetics (PK) scientist.

The Early Development Lead and Medical Monitor must be in attendance and cannot be represented by a voting designee or delegate. Voting designees can be identified as appropriate by the GSO or Site Investigator(s). A Site Investigator may identify a delegate (eg, sub-Investigator) who is listed in the Delegation of Authority. If a Site Investigator does this, the Site Investigator must provide written agreement with the designee or delegate's vote.

For a DLRM to occur, the Early Development Lead and Medical Monitor must attend, and the GSO or delegate must attend. In addition, a quorum of Site Investigators must be present. A quorum is defined as more than 50% of the participating investigators or their qualified designee. The DLRM will be rescheduled if these requirements are not met.

All available study data, including demographics, investigational product administration, medical history, concomitant medications, adverse events, electrocardiogram (ECG), vital signs, and laboratory results will be reviewed. Data to be reviewed will be unqueried.

DLRM voting will occur as follows: there will be a total of 4 votes, 1 for Early Development Lead, 1 for the Medical Monitor, 1 for the GSO or delegate, and 1 for all of

Approved

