**Date:** 25 August 2020 **Page 9 of 35** 

This study will use a staggered enrollment approach. Subject enrollment will start with cohort 1 (Section 3.1.1). The first subject dosed in cohort 1 will serve as the sentinel subject. Subsequent subjects dosed in cohort 1 will start AMG 330 ( μg/day) administration once sentinel subject has cleared the study day 21 dose (AMG 330 monotherapy at \(\begin{align\*}
\text{ug/day}\). Per sponsor determination, if the sentinel subject does not experience a dose-limiting toxicity (DLT) on days 15 to 21 after pembrolizumab is administered, the other subjects in cohort 1 will be allowed to continue the planned treatment schedule. If the sentinel subject experiences a DLT during days 15 to 21, the dose level review team (DLRT) will discuss the case and the decision will be made by the sponsor based on clinical assessments of the adverse event and potential decisions by the sponsor may include stopping AMG 330 and/or pembrolizumab, dose de-escalation of AMG 330, or continuing therapy at full dose. Investigators and sponsor will meet after all subjects in cohort 1 have completed study day 28 (ie, AMG 330 µg/day dose level in combination with pembrolizumab) to assess the safety profile. If pre-specified safety criteria are met (≤ 3 out of 10 treated subjects in cohort 1 experienced DLT by day 28), subjects enrolled in cohort 2 (Section 3.1.2) may proceed with the treatment schedule. Similar to cohort 1, the first subject dosed in cohort 2 will serve as the sentinel subject. Per sponsor determination, if the sentinel subject does not experience a DLT during the first 7 days, the other subjects in cohort 2 will be allowed to continue the planned treatment schedule.

Safety data will be continuously monitored throughout the whole treatment period. Sponsor in consultation with investigators may reconvene to make appropriate safety measures and adjustments as needed.

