### 7. Planned Analyses

# 7.1 Interim Analysis and Early Stopping Guidelines

Safety data will be reviewed on an ongoing basis. The dose level review meeting (DLRM) will occur when at least 10 treated subjects in cohort 1 have been dosed through study day 28 to determine if the safety profile of initial steps in cohort 1 is acceptable to begin enrollment of cohort 2 or if the study should be stopped. If 3 or more of the 10 treated subjects in cohort 1 experience a DLT by day 28, the guidance to the DLRT is to recommend not to initiate cohort 2. The stopping rule is based on having at least a posterior probability of > 70% that the DLT rate is > 20% assuming a prior distribution of Beta (0.40, 1.60). If the true DLT rate is 10%, 20%, 30%, 40%, or 50%,

Protocol Number: 20170646

Date: 25 August 2020 Page 18 of 35

then the probability of stopping the study at the interim analysis is 7%, 32%, 62%, 83%, 95%, respectively.

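### The cohort 2 decision has two different triggers, and the plan does not say who is counted, or against what boundary, once more than 10 cohort 1 subjects have been treated

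*Protocol*

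**What the plan says.** One group of sections waits for the whole of cohort 1. Protocol 4.1 (and, in the same terms, the synopsis) says "Investigators and sponsor will meet after all subjects in cohort 1 have completed study day 28". Protocol 6.2.1 is stricter: "Cohort 2 will be initiated only after all subjects in cohort 1 completed study day 28". SAP 3.1 places the meeting "after all subjects in cohort 1 have completed study day 28".

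Another group sets a minimum number. Protocol 9.4.1.1: "A DLRM will occur when at least 10 treated subjects in cohort 1 have been dosed through study day 28". SAP 7.1 says the meeting "will occur when at least 10 treated subjects in cohort 1 have been dosed through study day 28". The criterion in protocol 11.3 is that "at least 10 treated subjects in cohort 1 have been dosed through the end of" the dose step finishing on day 28, and the same appendix says "a dose level review meeting (DLRM) will be conducted 1 time".

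Protocol 4.2 and 9.2 and SAP 3.2 give 10 as a minimum for cohort 1 and state no maximum. Protocol 4.2.1 allows replacement. Protocol 6.2.1 adds that a sentinel replaced after a DLT at the third AMG 330 step still has that DLT counted for the stopping rules. The boundary is always expressed out of 10. Its basis, in protocol 9.4.1.1 and SAP 7.1, is a posterior probability above 70% that the DLT rate exceeds 20%, with a Beta(0.40, 1.60) prior.

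**The concern.** This is the only numerical cohort-level safety check before cohort 2 starts both drugs together on day 1. If exactly 10 subjects are treated and all reach day 28, the two triggers select the same people at the same time. Otherwise they need not.

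The protocol foresees more than 10. Under 6.2.1, dosing stops for any DLT unless the investigator and sponsor agree to resume it. A subject whose dosing is not resumed is treated but not dosed through day 28, so reaching ten who are dosed through day 28 then means treating more than ten. Early withdrawals act the same way. Overlapping enrolment can also leave some subjects before day 28 when the tenth gets there.

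In each case the review team must decide whether these subjects enter the numerator, the denominator, both or neither, and then apply a boundary defined only for 10. The plan answers neither question.

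**Working it through.** **1. The plan's own figures.** With X DLTs among 10 subjects, X ~ Binomial(10, p), P(X ≥ 3) at p = 10, 20, 30, 40, 50% is 7.0, 32.2, 61.7, 83.3, 94.5%. This reproduces the stated 7, 32, 62, 83, 95%. At least 4 of 10 gives 1.3, 12.1, 35.0, 61.8, 82.8% and does not.

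**2. The boundary when n subjects are counted.** With x DLTs among n, the posterior is Beta(0.40 + x, 1.60 + n − x). The boundary is the smallest x for which P(rate > 0.20) exceeds 0.70.

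| n counted | Boundary | Posterior one DLT below | Posterior at boundary | P(stop) at 10/20/30/40/50% |
|---|---|---|---|---|
| 10 | 3 | 0.4418 | 0.7195 | 7.0 / 32.2 / 61.7 / 83.3 / 94.5% |
| 11 | 4 | 0.6640 | 0.8600 | 1.9 / 16.1 / 43.0 / 70.4 / 88.7% |
| 12 | 4 | 0.6084 | 0.8208 | 2.6 / 20.5 / 50.7 / 77.5 / 92.7% |
| 13 | 4 | 0.5539 | 0.7783 | 3.4 / 25.3 / 57.9 / 83.1 / 95.4% |
| 14 | 4 | 0.5013 | 0.7334 | 4.4 / 30.2 / 64.5 / 87.6 / 97.1% |

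Three DLTs meet the criterion among 10 subjects but not among 11 or more. For example, if three subjects stop early with a DLT and are not resumed, and ten others are dosed through day 28, 13 have been treated. Three of 13 has a posterior of 0.5539, whereas three set against a denominator of 10 has 0.7195.

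**3. How often the answer changes (illustration).** Assume 12 treated. One reading counts 10 of them (x DLTs); the other also counts the remaining 2 (y DLTs). Subjects are independent with the same by-day-28 DLT rate p.

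- *Posterior boundary (3 of 10, 4 of 12).* The readings differ if x = 3 and y = 0, or x = 2 and y = 2.
  - p = 20%: 0.2013 × 0.64 + 0.3020 × 0.04 = 0.141.
  - p = 30%: 0.2668 × 0.49 + 0.2335 × 0.09 = 0.152.
- *Fixed count of 3 at either size.* They differ if x = 2 and y ≥ 1, or x = 1 and y = 2.
  - p = 20%: 0.3020 × 0.36 + 0.2684 × 0.04 = 0.119 (0.1195 before rounding the terms, so about 12%).
  - p = 30%: 0.2335 × 0.51 + 0.1211 × 0.09 = 0.130.

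The direction depends on the rule. At p = 30%, counting all 12 moves the stopping probability from 61.7% down to 50.7% under the posterior boundary, and up to 74.7% under a fixed count of 3.

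**4. How often 10 is exceeded.** The documents give no rate. If each subject independently had a 5, 10 or 20% chance of not reaching day 28 (assumed values), the chance that at least one of the first 10 does not is 1 − 0.95^10 = 40%, 1 − 0.90^10 = 65%, or 1 − 0.80^10 = 89%.

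**The case against.** Four counter-arguments deserve weight.

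- **Later DLTs would be seen.** A reader might infer that, with one meeting, DLTs in subjects beyond the tenth never enter the decision. The documents do not support that. Protocol 11.3 has the team review all available study data, 9.4.1.1 keeps safety under ongoing review, the boundary is guidance, and under 6.2.1 the sponsor decides. What is missing is a rule for counting those subjects in the formal recommendation.
- **A fixed count of 3 applied to 12 or more is not in the plan.** A reader might infer that counting everyone raises stopping from about 62% to 75% at a 30% rate. No section applies at least 3 to a number above 10, and the plan's posterior criterion moves the probability the other way. The fixed-count figures are conditional only.
- **Replacement alone need not leave subjects pending.** Replacements are usually the last to reach day 28, and the early leavers' outcomes are then known. This stands for the timing. It does not settle whether early leavers belong in the denominator.
- **The posterior criterion applies at any n.** True, and the table above follows from it. But the operative rule is written as a count out of 10, and nothing says the criterion replaces that count at other sizes.

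It is also over-literal to say that waiting for all subjects becomes impossible once one leaves. The wording should nevertheless say what happens then.

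**Conclusion.** The point holds as an inconsistency between sections of the current documents, joined to an undefined counted set and boundary above 10 subjects. The stated operating characteristics describe only at least 3 of exactly 10.

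With 2 extra subjects counted or not, the formal recommendation differs in about 14% (true rate 20%) or 15% (30%) of trials under the posterior boundary, and 12% or 13% if a count of 3 were kept. These figures are conditional on exactly 2 such subjects, on independence and a common DLT rate, and on the extra subjects being either fully counted or fully left out. They are not the chance that this trial goes wrong, because the documents give no frequency for exceeding 10 and the team and sponsor may depart from the guidance.

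A separate conflict lies in the same sections: protocol 4.1 and 6.2.1 and SAP 3.1 let cohort 2 proceed with at most 3 of 10, while protocol 9.4.1.1 and SAP 7.1 advise against it at 3 or more. It adds nothing to the figures above, but resolving it alone would leave this point open.

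**What to change.** 1. Reconcile the synopsis, protocol 4.1, 6.2.1, 9.4.1.1 and 11.3, and SAP 3.1 and 7.1 to one trigger.
2. Define the counted set as cohort 1 subjects who have completed day 28 or had a DLT by day 28, including replaced subjects whose DLT counts. Subjects still before day 28 without a DLT are not added to the denominator. State how subjects who leave before day 28 without a DLT are handled.
3. Add the count boundary and stopping probabilities for each n from 10 to 14 from the stated posterior criterion, as tabulated above. The sponsor should note the step between 10 and 11 counted (61.7% to 43.0% at a 30% rate) and confirm that it is acceptable.
4. Reconcile at most 3 with at least 3 of 10 in the same revision.

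Simply counting everyone treated by the data cut would not do. One subject dosed the day before would turn 3 of 10 (0.7195, criterion met) into 3 of 11 (0.6640, not met) with no new safety information; cohort 1 subjects receive no pembrolizumab before day 15. Under the proposed set, a pending subject with a DLT enters ahead of pending subjects without one, which tilts the observed rate upward; waiting for those already dosed removes this.

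The cost is wording changes and a small table, possibly a short wait for subjects already dosed. No extra subjects are needed.
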